### 6.3. EXPLORATORY OBJECTIVES

- i. To describe the immunophenotype of SCLCs, assessed by immunohistochemistry and the associations with ORR, PFS and OS to each of the treatment arms.
  - a. For those patients treated in the pembrolizumab arm, pre-treatment samples also will be compared to on-treatment biopsy samples to identify the immunophenotype of response.
- ii. To describe the temporal change in T cell immunophenotypes in peripheral blood mononuclear cell samples and correlate with clinical response.
- iii. To explore the relationship between mutational burden and response to pembrolizumab therapy.
- iv. To identify candidate neoantigens and explore their associations with response to pembrolizumab therapy.
- v. To examine the changes in tumors that are associated with either response or resistance to study therapy by performing comparative analyses on matched specimens.

### 6.4. FUTURE BIOMEDICAL RESEARCH

All collected biospecimens will be stored in the Alliance Foundation Biorepository (AFB), a CAP-accredited biorepository at Washington University in St. Louis, until biospecimen accrual and clinical follow-up is sufficiently complete to allow for the design and execution of specific correlative analyses using 'state-of-the-art' analytical platforms that will be available at that time.

Such biomarker research will address emergent questions not described elsewhere in this protocol and will only be conducted on specimens from appropriately consented patients. The objective of collecting specimens for future biomedical research is to explore and identify biomarkers that inform the scientific understanding of disease and/or their therapeutic treatments in the context of this study. Proposals for future correlative research will undergo rigorous scientific, programmatic, and statistical review by AFT, and biospecimens will only be released to those investigators who have obtained appropriate regulatory approval and demonstrate adequate funding to successful complete proposed research aims. AFT will ensure that all collected specimens are used only for approved research protocols.

Anonymized (de-identified) data generated from biospecimens used for future correlative research, including somatic and constitutional (germline) genomic data, may be shared with other researchers or deposited in a publicly accessible or controlled-access data repositories. Correlative study results and data will never be returned to individual patients.

## 7. PATIENT SELECTION

### 7.1. INCLUSION CRITERIA

In order to be eligible for participation in this study, the patient must:

1. Have histologically or cytologically confirmed small cell lung cancer. Confirmation will be done at each participating site.
2. Have relapsed or progressed after only one prior chemotherapy regimen, which must have been an etoposide-platinum doublet. Eligible patients will be defined as follows:

**“Sensitive” Disease:** Patients who had one previous line of chemotherapy and relapsed after  $\geq 60$  days of completion of treatment.

**“Refractory” Disease:** Patients with no response to first-line chemotherapy or progression  $<60$  days after completing treatment.

3. Be  $\geq 18$  years of age on day of signing informed consent.
4. Have a life expectancy of at least 3 months.
5. Have a performance status of  $\leq 1$  on the ECOG Performance Scale.
6. Have measurable disease based on RECIST 1.1.
7. Have a tumor tissue specimen available from either a core or excisional biopsy. The tumor specimen should be of adequate size and tumor cellularity to perform whole exome sequencing and immunohistochemistry. In subjects for whom newly obtained samples cannot be obtained (e.g. tumor inaccessible or safety concern), archived tissue may be submitted, if it otherwise satisfies all specimen criteria. Archival samples must have been obtained within 42 days prior to signing consent (please refer to section 12.1 of protocol).
8. Demonstrate adequate organ function as defined in Table 1.

**Table 1. Adequate Organ Function Laboratory Values**

System	Laboratory Value
Hematological	
Absolute neutrophil count (ANC)	$\geq 1,500$ /mcL
Platelets	$\geq 100,000$ / mcL
Hemoglobin	$\geq 8$ g/dL (without transfusion)
Renal	
Serum creatinine	$\leq 1.5$ X upper limit of normal (ULN)
OR	OR
Glomerular Filtration Rate (GFR)	GFR $\geq 60$ mL/min* for patient with creatinine levels $> 1.5$ X institutional ULN

Hepatic	
Serum total bilirubin	$\leq 1.5 \times \text{ULN}$ OR Direct bilirubin $\leq \text{ULN}$ for patients with total bilirubin levels $> 1.5 \text{ ULN}$
AST (SGOT) and ALT (SGPT)	$\leq 2.5 \times \text{ULN}$ OR $\leq 5 \times \text{ULN}$ for patients with liver metastases
Albumin	$\geq 2.5 \text{ mg/dL}$
*GFR should be calculated per institutional standards.	

9. Female patients of childbearing potential should have a negative urine or serum pregnancy within 72 hours of starting treatment. If the urine test is positive or cannot be confirmed as negative, a serum pregnancy test will be required.
10. Female patients of childbearing potential must be willing to an adequate method of contraception as outlined in Section 14.4.1 – Contraception for the course of the study through 120 days after the last dose of study medication (see Section 13.4.1). Patients of childbearing potential are those who have not been surgically sterilized or have not been free from menses for  $> 1$  year.  
Note: Abstinence is acceptable if this is the usual lifestyle and preferred contraception for the subject.
11. Male patients must agree to use an adequate method of contraception as outlined in Section 14.4.1 – Contraception - starting with the first dose of study therapy through 120 days after the last dose of study therapy. Note: Abstinence is acceptable if this is the usual lifestyle and preferred contraception for the subject.

## 7.2. EXCLUSION CRITERIA

The patient must be excluded from participating in the study if the patient:

1. Is currently participating in or has participated in a study of an investigational agent or using an investigational device within 14 days of the first dose of treatment.
2. Has a diagnosis of immunodeficiency or is receiving systemic steroid therapy or any other form of immunosuppressive therapy within 7 days prior to the first dose of study treatment.
3. Has had a prior monoclonal antibody (mAb) within 4 weeks prior to study Day 1 or who has not recovered (i.e.,  $\leq$  Grade 1 or at baseline) from adverse events due to agents administered more than 14 days earlier.

4. Has had prior chemotherapy, targeted small molecule therapy, or radiation therapy within 2 weeks prior to study Day 1 or who has not recovered (i.e.,  $\leq$  Grade 1 or at baseline) from adverse events due to a previously administered agent.  
*Note: Patients with  $\leq$  Grade 2 neuropathy or  $\leq$  Grade 2 alopecia are an exception to this criterion and may qualify for the study.*
5. Has undergone major surgery, he/she must have recovered adequately from the toxicity and/or complications from the intervention prior to starting therapy.
6. Has a known additional malignancy that is progressing or requires active treatment.
7. Has known active central nervous system (CNS) metastases. Patients with previously treated brain metastases may participate provided they are stable (without evidence of progression by imaging for at least four weeks prior to the first dose of study treatment and any neurologic symptoms have returned to baseline), have no evidence of new or enlarging brain metastases, and are not using steroids for at least 7 days prior to study treatment.
8. Has known carcinomatous meningitis.
9. Has an active autoimmune disease requiring systemic treatment in the past 2 years or a documented history of clinically severe autoimmune disease, or a syndrome that requires systemic steroids or immunosuppressive agents. Patients with vitiligo or resolved childhood asthma/atopy would be an exception to this rule. Patients that require intermittent use of bronchodilators or local steroid injections would not be excluded from the study. Patients with hypothyroidism stable on hormone replacement or Sjorgen's syndrome will not be excluded from the study.
10. Has evidence of interstitial lung disease, or history of (non-infectious) pneumonitis that required steroids, or current pneumonitis.
11. Has an active infection requiring systemic therapy.
12. Has a history or current evidence of any condition, therapy, or laboratory abnormality that might confound the results of the study, interfere with the patient's participation for the full duration of the study, or is not in the best interest of the patient to participate, in the opinion of the treating investigator.
13. Has known psychiatric or substance abuse disorders that would interfere with cooperation with the requirements of the study.
14. Is pregnant or breastfeeding, or expecting to conceive or father children within the projected duration of the study, starting with the pre-screening or screening visit through 120 days after the last dose of study treatment.
15. Has received prior therapy with an anti-PD-1, anti-PD-L1, anti-CD137, or anti-Cytotoxic T-lymphocyte-associated antigen-4 (CTLA-4) antibody (including ipilimumab or any other antibody or drug specifically targeting T-cell co-stimulation or checkpoint pathways).

16. Has a known history of Human Immunodeficiency Virus (HIV) (HIV 1/2 antibodies).
17. Has known active Hepatitis B (e.g., HBsAg reactive) or Hepatitis C (e.g., HCV RNA [qualitative] is detected).
18. Has received a live vaccine within 30 days prior to the planned first dose of study therapy.  
*Note: Seasonal influenza vaccines for injection are generally inactivated flu vaccines and are allowed; however intranasal influenza vaccines (e.g., Flu-Mist®) are live attenuated vaccines, and are not allowed.*
19. Has a known history of active TB (Bacillus Tuberculosis).
20. Hypersensitivity to pembrolizumab or any of its excipients.
21. Patients with underlying or previous paraneoplastic syndromes

## 8. PATIENT ENROLLMENT

### 8.1. SITE ENROLLMENT REQUIREMENTS

#### Requirements for Site Enrollment

- IRB Certification
- IRB/Regulatory Approval

Submit completed forms along with a copy of your IRB Approval, Model Informed Consent and any other required documentation to the AFT eTMF system.

### 8.2. PATIENT ENROLLMENT REQUIREMENTS

**Informed consent:** The patient must be aware of the neoplastic nature of his/her disease and willingly consent after being informed of the procedure to be followed, the experimental nature of the therapy, alternatives, potential benefits, side-effects, risks, and discomforts. Current human protection committee approval of this protocol and a consent form is required prior to patient consent and enrollment.

### 8.3. PATIENT SCREENING, ENROLLMENT/RANDOMIZATION PROCEDURES

Patient enrollment will be facilitated using the AFT web-based IRT (interactive response technology) system.

Patients must be screened and sign informed consent prior to any study related testing, including submission of biospecimens. After written informed consent has been obtained, the study site will obtain a unique patient number or unique patient

identifier, which will stay the same throughout the entire study. Patients screened but not randomized for any reason have to be registered as a Screening Failure in IRT.

Prior to accessing AFT IRT, site staff should verify the following:

- All eligibility criteria have been met within the protocol stated time frames.
- All patients have signed an appropriate consent form and HIPAA authorization form (if applicable).
- Adequate tumor tissue will be available and can be sent to the AFT biorepository for central laboratory analysis within 14 days of randomization.

The AFT IRT system will provide the site with a printable confirmation of enrollment and treatment randomization information. Please print this confirmation for your records. The site will receive instructions for drug ordering via IRT, upon randomization.

#### **8.4. STRATIFICATION FACTORS AND TREATMENT ASSIGNMENTS**

Randomization will be stratified according to:

- 1) Sensitive Disease vs Refractory Disease:** sensitive disease will be defined as those patients with disease progression who relapse after treatment with standard first-line etoposide/platinum  $\geq 60$  days from completing chemotherapy, and refractory disease will be defined as patients with disease progression  $< 60$  days from completing chemotherapy.

This is an open-label study; therefore, AFT, the investigator and patient will know the treatment administered.

## 9. SCHEDULE OF ASSESSMENTS

### 9.1. SCHEDULE OF ASSESSMENTS

**Table 2. Schedule of Assessments**

Study Period:	Treatment Cycles 								End of Treatment §	Post-Treatment Evaluations			
	Treatment Cycle/Title:	Screening (Visit 0)	1	2	3	4	To be repeated beyond 8 cycles			At time of treatment discontinuation	Safety Follow-up 	Follow Up Visits 	Survival Follow-Up 
5							6	7	8				
Scheduling Window (Days)  :	-14 to -1		± 3	± 3	± 3	± 3	± 3	± 3	± 3	At time of treatment discontinuation	30 days	Every 6 weeks	Every 12 weeks
Informed Consent 	X												
Inclusion/Exclusion Criteria 	X												
Demographics	X												
Medical History 	X	X	X	X	X	X	X	X	X	X	X	X	X
Prior and Concomitant Medication Review 	X	X	X	X	X	X	X	X	X	X			
SCLC Disease Details 	X												
Study Treatment Administration		X	X	X	X	X	X	X	X				
Review Adverse Events 		X	X	X	X	X	X	X	X	X	X	X	X
Physical Examination	X	X	X	X	X	X	X	X	X		X	X	
Vital Signs and Weight 	X	X	X	X	X	X	X	X	X	X	X	X	X
ECOG Performance Status	X	X	X	X	X	X	X	X	X	X	X	X	X
Pregnancy Test – Urine or Serum β-HCG 	X	X											
PT/INR and aPTT 	X												
CBC with Differential 	X		X	X	X	X	X	X	X	X	X		
Comprehensive Serum Chemistry Panel 	X		X	X	X	X	X	X	X	X	X		
Urinalysis 	X				X				X	X			

Study Period:	Treatment Cycles 									End of Treatment §	Post-Treatment Evaluations		
Treatment Cycle/Title:	Screening (Visit 0)	1	2	3	4	To be repeated beyond 8 cycles				At time of treatment discontinuation	Safety Follow-up 	Follow Up Visits 	Survival Follow-Up 
						5	6	7	8				
Scheduling Window (Days)  :	-14 to -1		± 3	± 3	± 3	± 3	± 3	± 3	± 3	At time of treatment discontinuation	30 days	Every 6 weeks	Every 12 weeks
T3, FT4 and TSH 	X		X		X		X		X	X			
EKG	X												
Tumor Imaging (CT Scan/MRI) 	X		X		X		X		X	X		X	
Archival or Newly Obtained Tissue Collection 	X												
Newly Obtained Tissue Collection	X 		X 							X 			
Correlative Studies Blood Collection 	X		X		X		X		X				

-  In general, assessments/procedures are to be performed on day 1 and prior to the first dose of study treatment for each cycle unless otherwise specified. Treatment cycles are 3 weeks (21-days); however the treatment cycle interval may be increased due to toxicity according to the dose modification guidelines provided in Section 13. If treatment cycles are increased all procedures except imaging will be completed according to cycle number and not weeks on treatment, imaging will be performed every 6 weeks ( $\pm 7$  days) from the first dose of study treatment regardless of any treatment delays during the first 8 cycles.
-  In general, the window for each visit is  $\pm 3$  days unless otherwise specified.
-  Written consent must be obtained prior to performing any protocol specific procedure. Results of a test performed prior to the patient signing consent as part of routine clinical management are acceptable in lieu of a screening test if performed within the specified time frame. Informed consent and assessment of eligibility criteria can be obtained 21 days prior to the start of treatment.
-  Medical history should be completed by study staff and include all comorbidities, as well as a detailed assessment of smoking history: number of years of tobacco smoke, packs of cigarettes smoked, ongoing tobacco smoke or time since quitting smoking. This will also include documentation of SCLC disease status.
-  Prior medications – record all medications taken within 14 days of visit 1 and all treatments for a prior cancer other than SCLC. After the Safety Follow-up Visit record all medications taken for SAEs and ECIs as defined in Section 17.
-  Disease details are to be collected, including: sites of disease; first-line chemotherapy (cisplatin vs carboplatin); number of cycles of first-line chemotherapy; administration of prophylactic cranial irradiation, consolidative mediastinal radiation or palliative radiation to an osseous site; best response to prior therapy (stable disease, partial response, complete response, progression of disease); time to relapse (sensitive disease vs resistant disease).
-  AEs and laboratory safety measurements will be graded per NCI CTCAE version 4.0. All AEs, whether gradable by CTCAE or not will also be evaluated for seriousness.
-  All AEs of unknown etiology associated with study treatment exposure should be evaluated to determine if it is possibly an ECI.
-  Vital signs to include: temperature, pulse, respiratory rate, weight and blood pressure. Height will be measured at visit 1 only.
-  For women of reproductive potential, a urine pregnancy test will be performed within 72 hours prior to the first dose of study treatment. If urine pregnancy results cannot be confirmed as negative, a serum pregnancy test, performed by the local study site laboratory, will be required. Pregnancy tests (serum and/or urine tests) should be repeated if required by local guidelines.
-  Coagulation factors (PT/INR and aPTT) should be performed if clinically indicated and monitored closely throughout the study for any patient receiving anticoagulant therapy.
-  Laboratory tests for screening are to be performed within 14 days prior to the first dose of study treatment. See Table 3 for details regarding laboratory tests.
-  After Cycle 1, lab samples can be collected up to 72 hours prior to the scheduled time point. Laboratory results must be known and acceptable prior to dosing.
-  Perform urinalysis every 4 cycles.
-  Required at baseline. Perform thyroid testing every other cycle while patients are receiving pembrolizumab.

-  Baseline tumor imaging will include the following: CT chest and abdomen with contrast OR CT chest without contrast and MRI abdomen with/without gadolinium and imaging of other known sites of disease; and brain imaging with MRI with/without contrast (or CT with contrast if the patient cannot tolerate an MRI). Imaging of the pelvis should be performed as clinically indicated or if there is known metastases in the pelvis. The initial tumor imaging will be performed within 14 days prior to the first dose of study treatment. Scans performed as part of routine clinical management are acceptable for use as the screening scan if they are of diagnostic quality and performed within 14 days prior to the first dose of study treatment. On-study imaging will be performed every 6 weeks ( $42 \pm 7$  days) after the first dose of study treatment or more frequently if clinically indicated. **The timing for imaging studies should follow calendar days and should not be adjusted for delays in cycle starts or extension of topotecan or pembrolizumab cycle frequencies.** The same imaging technique should be used in a patient throughout the study. Local reading (investigator assessment with site radiology reading) will be used to determine eligibility and for patient management.
-  After first documentation of progression (if the patient is clinically stable) or response per RECIST 1.1 repeat imaging for confirmation is required. Confirmatory imaging may be performed as early as 28 days later; alternatively, the scan performed at the next scheduled time point may be used as confirmation.
-  Tumor tissue for biomarker analysis from an archival tissue sample (not more than 42 days prior to signing consent) or newly obtained tumor tissue from a recent biopsy of a tumor lesion not previously radiated. Please see AFT 17 Correlative Science Manual for specimen collection instructions. If a NEW biopsy is performed, the investigator should ensure that adequate tissue is collected.

-  Patients who discontinue study treatment for a disease progression, will undergo a mandatory Safety Follow-up Visit approximately 30 days after the last dose of study treatment or before the initiation of a new antineoplastic treatment, whichever comes first. Patients with an AE of grade > 1 will be further followed until the resolution of the AE to Grade 0-1 or until beginning of a new antineoplastic therapy, whichever occurs first.
-  Patients who discontinue study treatment for a reason other than disease progression will move into the Follow-up Phase and should be assessed every 6 weeks ( $42 \pm 7$  days) by radiologic imaging to monitor disease status, development of drug related SAEs and ECIs/irAEs, and initiation of a new antineoplastic therapy. Follow-up visit 1 should be scheduled 6 weeks after the last dose of study treatment. Unless otherwise noted in the flow chart, every effort should be made to collect patient information until the start of new antineoplastic therapy, disease progression, or death, whichever comes first.
-  Once a patient experiences disease progression or starts a new antineoplastic therapy, the patient moves into the Survival Follow-up Phase and should be contacted by telephone every 3 months to assess for survival status, development of drug related SAEs and ECIs/irAEs and the start of new antineoplastic therapy if applicable.
-  Record all AEs occurring within 30 days after the last dose of study treatment or until initiation of a new antineoplastic therapy, whichever comes first. Report all SAEs (related and unrelated to study treatment) occurring within 90 days of the last dose of study treatment or the start of new anti-cancer treatment, whichever comes first. All ECIs/irAEs occurring within 90 days of the last dose of study treatment should be reported regardless of initiating new anticancer therapy. After this time, report only SAEs and ECIs/irAEs that are considered related to study treatment.
-  If archival sample is not available, fresh tissue samples will be collected for correlative studies.
-  Those patients receiving pembrolizumab will undergo a biopsy obtained during week 4 to 6 of treatment for biomarker analysis, if clinically feasible and safe. A tumor lesion not previously radiated (required for PD-L1 determination) should be biopsied. The tumor sample must be sent to the AFT-Biorepository. See AFT 1 Correlative Science Manual for additional details.
-  Patients on the topotecan arm who progress and are to cross-over to the pembrolizumab arm, will undergo a biopsy just before initiating experimental treatment, if clinically feasible and safe. A tumor lesion not previously radiated (required for PD-L1 determination) should be biopsied. The tumor sample must be sent to the AFT-Biorepository.
-  Whole blood samples for genomic analyses, and peripheral blood cell/serum plasma samples for correlatives will be collected for all patients at screening, at week 4-6 biopsy, at imaging during all cycles, and at progression/cross-over. Samples will be collected per Section 12. Note that each time point requires differing types of blood collection. Please refer to the lab manual for detailed instructions on sample collection. § For patients who cross-over from the topotecan arm to the pembrolizumab arm, they will undergo the same assessments and procedures from study start, except that a repeat tumor biopsy will not be performed during weeks 4 to 6.

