### **17. ADVERSE EVENTS**

An adverse event (AE) is defined as any untoward medical occurrence in a patient or clinical investigation subject administered a pharmaceutical product and which does not necessarily have to have a causal relationship with this treatment. An adverse event can therefore be any unfavorable and unintended sign (including an abnormal laboratory finding, for example), symptom, or disease temporally associated with the use of a medicinal product or protocol-specified procedure, whether or not considered related to the medicinal product or protocol-specified procedure. Any worsening (i.e., any clinically significant adverse change in frequency and/or intensity) of a preexisting condition that is temporally associated with the use of pembrolizumab is also an adverse event.

Changes resulting from normal growth and development that do not vary significantly in frequency or severity from expected levels are not to be considered adverse events. Examples of this may include, but are not limited to onset of menses or menopause occurring at a physiologically appropriate time.

Adverse events may occur during the course of the use of pembrolizumab (or topotecan) during this study, or as prescribed in clinical practice, from overdose (whether accidental or intentional), from abuse and from withdrawal.

Progression of small cell lung cancer is not considered an adverse event unless it is considered to be drug related by the investigator.

The prompt reporting of adverse events is the responsibility of each investigator engaged in clinical research, as required by Federal Regulations. Adverse events must be described and graded using the terminology and grading categories defined in the NCI's Common Terminology Criteria for Adverse Events (CTCAE), Version 4.0. The CTCAE is available at [ctep.cancer.gov/protocolDevelopment/electronic\\_applications/ctc.htm](http://ctep.cancer.gov/protocolDevelopment/electronic_applications/ctc.htm). Attribution to protocol treatment for each adverse event must be determined by the investigator and reported on the required forms, using the codes provided.

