## 20. STATISTICAL ANALYSIS PLAN

The primary analysis will include all randomized patients but exclude ineligible patients or patients who cancel this study before receiving any protocol treatment.

The primary efficacy endpoint is PFS, which is defined as the time from the date of randomization to the date of earliest radiographic disease progression or death. If the subject does not experience radiographic disease progression or death, then the data will be censored at the date of the last disease assessment. PFS will be analyzed by Kaplan Meier methodology and compared between arm E and arm C, using a log-rank test stratified by disease type (sensitive vs refractory). A two-sided, stratified log-rank test P value will be provided. Median PFS time will be calculated and 95% confidence interval for median PFS will be presented. Overall survival (OS) will be analyzed in a similar manner as PFS.

Late treatment effect is often expected for immunotherapy. For this reason, a weighted log rank test with Harrington-Fleming weights that optimize the expected late treatment effect will be conducted as a supplementary analysis for both PFS and OS. In particular, the following three parameter settings will be used: (1)  $\rho = 0$  and  $\gamma = 0.5$ ; (2)  $\rho = 0$  and  $\gamma = 1$ ; and (3)  $\rho = 0$  and  $\gamma = 2$  (39).

The proportion of subjects with objective response as assessed by the investigator using RECIST version 1.1 will be evaluated for randomized subjects. The objective response rate will be estimated and compared between arm E and arm C, using a Cochran-Mantel-Haenszel (CMH) test stratified by tumor volume. A two-sided, stratified CMH test P value will be provided. In addition, a 95% confidence interval will be constructed for the estimated proportions. Similar analysis will be conducted for disease control rate (DCR), which is defined as the proportion of patients achieving complete, partial and stable disease after the protocol treatment.

All subjects who receive at least one dose of the study drug will be included in safety analysis. Treatment-related toxicity will be summarized by grade, type and system organ

class. Comparisons of the percentages of subjects experiencing an adverse event between arm E and arm C will be performed using Fisher's exact test.

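### On-treatment thyroid testing is scheduled only for patients receiving pembrolizumab, so a between-arm Fisher test on laboratory-only thyroid events leans towards an excess in arm E

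*Combined protocol and SAP*

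**What the plan says.** - **Thyroid tests.** Section 9.1, Table 2, has one row for T3, FT4 and TSH, with marks at screening, cycles 2, 4, 6 and 8, and end of treatment. The row is not split by arm. Footnote 15 requires the baseline test and then restricts the on-treatment ones: "Perform thyroid testing every other cycle while patients are receiving pembrolizumab". It does not mention the end-of-treatment mark.
- **Biopsies.** Footnote 24: "Those patients receiving pembrolizumab will undergo a biopsy obtained during week 4 to 6 of treatment for biomarker analysis, if clinically feasible and safe". Footnote 25: "Patients on the topotecan arm who progress and are to cross-over to the pembrolizumab arm, will undergo a biopsy just before initiating experimental treatment", again if feasible and safe.
- **After cross-over.** The note to Table 2 says of these patients that "they will undergo the same assessments and procedures from study start", with the week 4-6 biopsy left out. Thyroid testing therefore starts for them at that point.
- **What counts as an adverse event.** Section 17 includes an abnormal laboratory finding, and events "temporally associated with the use of a medicinal product or protocol-specified procedure", whether or not judged related. Section 17.1 records new events from randomization and sets no minimum grade. Table 13 places purely diagnostic observations in Grade 1.
- **Analysis.** Section 20: "Comparisons of the percentages of subjects experiencing an adverse event between arm E and arm C will be performed using" Fisher's exact test, among patients who received at least one dose. It makes no allowance for differing test schedules. It does not say whether events after cross-over count, or for which arm.

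**The concern.** An asymptomatic thyroid abnormality becomes an adverse event only if someone measures thyroid function. In arm E it is looked for at every second cycle. In arm C no on-treatment test is scheduled during the randomized period. If the plan is followed exactly, a Fisher test on a laboratory-driven thyroid row compares an arm that was searched with one that was searched little or not at all. A significant excess in arm E could then reflect the testing schedule and not the drug.

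Safety and tolerability of pembrolizumab is a secondary objective (Section 6.2). A p-value on such a row would look like evidence about the drug when part of it is an effect of ascertainment.

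**Working it through.** **Plan's own figures.** The documents give no figure for the adverse-event comparison. The nearest is the primary PFS power of about 82% (Section 19.1). With 86 events, hazard ratio 0.60, one-sided 0.10 and 2:1 allocation, Schoenfeld's formula gives Φ(√(86 × 2/3 × 1/3) × |ln 0.60| − 1.282) = Φ(2.233 − 1.282) = 0.83. With the stated 59/27 event split it gives 0.82. The figure is reproduced, and this point does not touch it.

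**Inputs.** From Section 19.1: 62 patients in arm E, 31 in arm C; median PFS 20 and 12 weeks, exponential. Assumed, because the documents are silent: two-sided 0.05 for adverse-event tests; the true rate r of laboratory-detectable thyroid abnormality, equal in both arms; and the share s of those abnormalities that arm C detects.

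**1. How unequal is the testing?** Cycles 2, 4, 6 and 8 start at weeks 3, 9, 15 and 21. With treatment to progression, the proportion still on treatment at week t is 2^(−t/median).
- Arm E: 0.901 + 0.732 + 0.595 + 0.483 = 2.71 tests per patient, about 168 in 62 patients.
- Arm C: 0.841 + 0.595 + 0.420 + 0.297 = 2.15 would fall due per patient, about 67 in 31 patients. Under footnote 15 none is scheduled.

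**2. How few events suffice?** With none seen in arm C, 7 of 62 in arm E gives two-sided Fisher p = 0.091 and 8 of 62 gives p = 0.0485. For the latter, the probability that all eight fall in arm E is C(62,8)/C(93,8) = 0.033, and the opposite tail adds 0.015.

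**3. Chance of a falsely significant excess in arm E.** Take X ~ Bin(62, r) in arm E and Y ~ Bin(31, r·s) in arm C. Sum the joint probability over all tables with p < 0.05 and X/62 > Y/31. For s = 0 this is simply P(X ≥ 8).

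| True rate r | equal detection | C detects half | C detects a quarter | C detects none |
|---|---|---|---|---|
| 5% | 0.2% | 0.5% | 0.8% | 1.2% |
| 10% | 1.2% | 5.9% | 13.0% | 27.8% |
| 15% | 1.4% | 10.5% | 28.0% | 73.1% |
| 20% | 1.8% | 16.9% | 42.4% | 94.7% |

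The nominal level in this direction is 2.5%. At a 5% rate the test stays below it throughout.

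**4. Any-event test.** Suppose 90% of patients in both arms have some event anyway, and 10% of the remaining arm E patients gain one from testing (0.90 + 0.10 × 0.10 = 0.91). The chance of a false excess moves from 2.0% to 2.9%. At an 80% base rate it moves from 2.0% to 3.5%.

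**5. Biopsy.** In arm E, 2^(−6/20) = 0.81 to 2^(−4/20) = 0.87 are progression-free at weeks 4-6. Assume 50-80% feasibility, a 5-20% complication rate and, for arm C, 50-80% cross-over.
- Arm E: 0.81 × 0.5 × 0.05 = 2% to 0.87 × 0.8 × 0.20 = 14% of patients affected.
- Arm C: 0.5 × 0.5 × 0.05 = 1% to 0.8 × 0.8 × 0.20 = 13%.

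**The case against.** The strongest counter-case has five parts.

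- **Arm C is not blind to thyroid events.** A reader might infer that arm C cannot show them at all. The documents do not support that. Symptomatic events are recordable in both arms, and Table 2 marks an end-of-treatment thyroid test without an arm split. This part stands: the no-detection column is an extreme, and persistent abnormalities could be caught at the end of treatment if that test is done in arm C.
- **The biopsy is not a one-arm procedure.** A reader might see the week 4-6 biopsy as an equal source of bias. Arm C patients who cross over also have a biopsy, normally within the 30-day recording window of footnote 22, and the ranges above nearly coincide. This part largely stands. One gap remains: footnote 22 can also close the window when new antineoplastic therapy starts, and the plan does not say whether cross-over pembrolizumab counts as that.
- **The test may cover treatment-related events only.** The sentence before it in Section 20 concerns treatment-related toxicity. If so, biopsy complications largely drop out. Thyroid findings would not: the relatedness questions in Table 13 ask whether pembrolizumab caused the event and whether it fits the known profile, so a thyroid finding in arm E is likely to be called related.
- **The important rows are safe.** A reader might extend the concern to the whole safety comparison. Step 4 shows little effect on an any-event test when most patients have an event. The pre-specified thyroid event of clinical interest is Grade 3 or higher (Section 3.3.2), while asymptomatic findings are Grade 1 by Table 13. This part stands.
- **The magnitude rests on assumptions.** True: rates, detection share and significance level are all assumed. Longer treatment in arm E would also make equal cumulative rates unlikely, even with identical testing.

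Nor does cross-over restore the balance. If later events were counted in arm C, events arising on pembrolizumab would be credited to the topotecan arm.

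**Conclusion.** The concern holds for laboratory-only thyroid events. They are much less likely to be found in arm C, and Section 20 allows them to be tested between arms as if both had been examined alike. At assumed true rates of 10-20%, the false-excess probability is 6-17% if arm C detects half and 28-95% if it detects none, against 1-2% with equal detection. At 5% there is no practical effect. These figures illustrate sensitivity and do not predict this trial's result. The detection share depends partly on an end-of-treatment test whose status in arm C the documents leave unclear.

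The point does not extend to the any-event comparison, the Grade 3 or higher thyroid event, the biopsy (a minor asymmetry) or the primary PFS analysis. It is a secondary safety-reporting defect, worth correcting because the correction is cheap.

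**What to change.** Add to Section 20:

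- Thyroid laboratory abnormalities without symptoms or treatment are tabulated by arm, with the number of patients tested after baseline, and without a between-arm p-value. They stay in the overall adverse-event tables.
- Symptomatic or treated thyroid events remain in the Fisher comparison.
- Events attributed to a research biopsy are flagged on the adverse-event form and listed separately by arm.
- The E v C comparison uses events with onset before cross-over pembrolizumab; later events are shown separately.
- State whether the Fisher test covers all adverse events or only treatment-related ones.

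In Section 9.1, reconcile footnote 15 with the end-of-treatment thyroid mark in Table 2, so that it is clear whether the mark applies to topotecan patients.

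**Cost.** Analysis-plan wording, one footnote clarification and one or two flags on the adverse-event form (thyroid event symptomatic or treated; biopsy attribution). The analysis changes need no extra tests or visits. What is lost is a formal p-value for laboratory-only thyroid events. Keeping those events in the overall tables matters, because some may be caused by the drug and should not disappear from view.
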